### 4.6 Limitations

The study had a single-arm design without a control group, a relatively small sample size ( $n=23$ ), and a short duration (6 weeks). Future research should employ randomized controlled trial designs with larger, more diverse populations.

## 5. CONCLUSIONS

This study provides strong evidence supporting the efficacy and safety of the BPIT 5-Line protocol for improving physical performance and reducing injury risk. The BPIT method is a valuable addition to the strength and conditioning field.

## APPENDICES

### APPENDIX A: Registration

- ClinicalTrials.gov ID: NCT[To be inserted post-registration]

**Appendix B:** Complete Participant Data (See attached file: *participant\_data\_with\_changes.csv*)

**Appendix C:** Statistical Analysis Results (See attached file: *statistical\_results.csv*) **Appendix**

**D:** Study Protocol (See attached file: *BPIT-GFFI-2024-001\_Protocol\_v1.0.md*)

If you have the actual NCT number or the journal/publisher details for the DOI prefix, I can insert them to make the document even more complete.

### APPENDIX: REGISTRATION & ARCHIVING

#### Registration Statement

- ClinicalTrials.gov: NCT[pending] (registration in progress)
- Zenodo DOI: [pending] – Full dataset, protocol, and report archived
- Primary Completion: November 30, 2024
- Results Submission Due: November 30, 2025

## 1. Objectives (directly from protocol)

Primary

- To assess change from baseline to Week 6 in 1-repetition maximum (1RM) for squat, bench press, and deadlift
- To assess the incidence of training-related injuries over the 6-week period

Secondary

- Change in resting heart rate and heart rate variability (HRV – RMSSD)
- Change in heart rate recovery (HRR) – if measured
- Change in muscle activation (EMG %MVC) for rectus abdominis and quadriceps
- Change in knee valgus angle and spinal curvature (degrees)

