## 1.3 Study Objectives

- **Primary Objective:** To assess the efficacy of the 6-week BPIT protocol in improving maximal strength (1RM) and reducing the incidence of training-related injuries.
- **Secondary Objectives:** To evaluate the impact on heart rate variability (HRV), heart rate recovery (HRR), muscle activation patterns (EMG), and joint biomechanics (knee valgus, spinal curvature).

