## 2.5 Outcome Measures

- **Primary:** Change in 1RM (squat, bench press, deadlift); Incidence of training-related injuries.
- **Secondary:** Change in HRV (RMSSD); Change in HRR; Change in EMG (rectus abdominis, quadriceps); Change in knee valgus angle and spinal curvature.

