## 2. Analysis Populations

- Intention-to-Treat (ITT): All 23 enrolled participants
- Per-Protocol (PP): Participants with  $\geq 80\%$  session adherence (actual adherence was 94.9%, so PP  $\approx$  ITT)
- Safety population: All participants who received at least one training session

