#### **6. Missing Data**

No missing primary outcome data expected (all 23 participants completed the study). If any missing values occur, listwise deletion will be used (sensitivity analysis with last-observation-carried-forward if  $>5\%$  missing).

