#### **10. Tables & Figures (to be produced)**

Exactly the same tables and figures that already appear in your final report (Tables 2–5, Figures 1–4).

Approved by:

---

[name] (PI)

---

Date: 30 November 2024

---

[name] (Statistician)

---

Date: 30 November 2024

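### Heart rate recovery is a listed secondary outcome without condition in Protocol 1.3 and 2.5, is made conditional in a SAP dated at primary completion, and has neither a result nor an explanation in the report body

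*SAP*

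**What the plan says.** The Protocol document is written as a completed study report. Its section 1.3 names among the secondary objectives "heart rate variability (HRV), heart rate recovery (HRR), muscle activation patterns (EMG". Section 2.5 gives the secondary outcomes as "Change in HRV (RMSSD); Change in HRR; Change in EMG (rectus abdominis, quadriceps" and then the two joint measures. Neither place attaches a condition to HRR.

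SAP 1, which presents its objectives as taken from the protocol, has "Change in heart rate recovery (HRR) – if measured". No other outcome there carries a condition.

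The SAP was approved with both lines reading "Date: 30 November 2024". The registration appendix of the Protocol document has "Primary Completion: November 30, 2024". SAP 2 reports that "actual adherence was 94.9" per cent, SAP 6 that "all 23 participants completed the study", and SAP 10 defines the outputs as "Exactly the same tables and figures that already appear in your final report", namely Tables 2–5 and Figures 1–4.

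SAP 5 has every continuous secondary endpoint analysed in the same way as the primary ones. In the report, 3.3.1, Table 3 and the caption of Figure 2 cover resting heart rate and HRV only.

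**The concern.** A conditional outcome is ordinary in a plan written before data collection. Here the plan was approved when participation was known to be complete and a report existed, so the condition leaves open something that could have been stated as fact. Following SAP 1 and SAP 10 as written allows a listed secondary outcome to drop out without anyone recording why.

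A reader of the report body cannot distinguish an outcome that was never collected from one that was collected and not shown. The first needs an explanation. The second would be a selective-reporting risk. Meanwhile the Executive Summary and the Discussion claim significant improvement on everything that was measured. That wording is compatible with HRR not having been measured, but it gives no notice that a listed outcome has no result.

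**Working it through.** There is no planned figure to reproduce. The check is a trace of each outcome through the lists and the results.

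| Measure | Protocol 2.5 | SAP 1 | Result in report body |
|---|---|---|---|
| Squat, bench press, deadlift 1RM (3) | yes | yes | Table 2 |
| Injury incidence (1) | yes | yes | 3.2.2, text only |
| HRV (1) | yes | yes | Table 3 |
| **HRR (1)** | **yes** | **conditional** | **none** |
| EMG, two muscles (2) | yes | yes | Table 5 |
| Knee valgus, spinal curvature (2) | yes | yes | Table 4 |
| **Resting heart rate (1)** | **no** | **yes** | **Table 3** |

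**Counts**
- Protocol 2.5: 3 + 1 + 1 + 1 + 2 + 2 = 10 measures (4 primary, 6 secondary).
- SAP 1: 10 + 1 (resting heart rate) = 11 measures (4 primary, 7 secondary).
- Reported: table rows 3 + 2 + 2 + 2 = 9, plus injury incidence = 10.
- In 2.5 and reported: 10 − 1 = 9 of 10; secondary only, 5 of 6. The missing one is HRR.
- In SAP 1 and reported: 11 − 1 = 10 of 11; secondary only, 6 of 7. The missing one is again HRR, which is also the only conditional item.
- Reported but not in 2.5: 1 of 10, resting heart rate (change −6.02 bpm, d −4.01).

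**Was the answer knowable?** The SAP approval date and the primary completion date are the same day, a difference of 0 days. The date alone would be weak evidence. Together with the observed adherence, the completion of all 23 participants and the reference to existing tables, it shows that the SAP was written with the study's conduct known. The tabulated outcomes are measured at baseline and Week 6. On the assumption that HRR was meant to follow the same schedule, it had by then either been collected or not.

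**Is a reason given?** Section 4.6 names three limitations: the single arm, the sample of 23 and the 6-week duration. HRR is not among them, and 3.3.1 does not mention it.

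**Does the effect-size range help?** The absolute d values in Tables 2–5, sorted, are 2.97, 3.12, 3.44, 3.91, 4.01, 4.01, 4.05, 4.65 and 4.76. The range in the Discussion, 2.97 to 4.76, is therefore fully explained by the nine tabulated outcomes. It does not settle the question, because an HRR effect inside that range would leave it unchanged.

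**Do SAP 5 and SAP 10 conflict?** Only if HRR was collected. SAP 5 would then require an analysis for which SAP 10 lists no table or figure. A result in text would still be possible, as for injury incidence.

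**The case against.** The strongest reply is that the documents lean towards HRR never having been measured. SAP 1 flags the possibility openly, SAP 10 lists no HRR output, and the summary claim is confined to what was measured. This stands as far as it goes: the pattern is consistent with non-collection, but does not establish it.

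A reader might infer something stronger in either direction. One inference is that HRR was measured and left out because the result was unfavourable. Nothing in the documents supports that. The other is that the trial departed from its protocol without disclosure. That is also too strong, because SAP 1 does signal that HRR may be unmeasured, and because the protocol proper, v1.0, is a separate attachment (Appendix D) that was not available. If v1.0 makes HRR conditional, SAP 1 follows it, and what remains is an inconsistency with 1.3 and 2.5 of the report. If v1.0 lists resting heart rate, that outcome was not added.

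It can also be said that the participant data (Appendix B) or the statistical results (Appendix C) may contain the answer. They may, and checking them comes first. An answer there would still leave the report body silent and SAP 1 unresolved.

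Finally, this is one secondary outcome in a study that SAP 7 calls exploratory, and no reported number is affected. That bears on the weight of the point, not on whether it is correct.

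**Conclusion.** The point holds as an outcome-reporting inconsistency, limited to the report body and the SAP. One of the 10 measures in Protocol 2.5 has no result and no stated reason, and the SAP left its status open when that status could have been stated. Whether HRR was collected is unknown from these documents, and no conclusion about motive or departure should be drawn.

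No currently reported figure changes, and the d range would change only if an HRR effect fell outside 2.97 to 4.76. The secondary mismatch, resting heart rate reported but absent from 1.3 and 2.5, is real within the report and depends on v1.0 for its meaning. This should be corrected, but it does not by itself undermine the other results. Confidence is high for the textual inconsistency and does not extend to any explanation of it.

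**What to change.** 1. Check Protocol v1.0 and the Appendix B and C files for HRR and resting heart rate.
2. Add a dated addendum to the SAP, keeping the approved text, that states whether HRR was collected.
3. If it was collected, analyse it under SAP 5 and report it in 3.3.1 or Table 3: mean and SD at both visits, mean change, 95% CI, p-value and paired d. Add the output to SAP 10. Table 3 has no confidence-interval column, so the interval needs a new column or a place in the text.
4. If it was not collected, say so with the reason in 3.3.1 and 4.6.
5. In the Executive Summary and Discussion, limit the claim of statistically significant improvement to named continuous outcomes that were tested. Injury incidence must not fall under it: 1/23 has no baseline, comparator or test. Tables 2 and 5 print no p-values, so these need to be shown if the claim is to cover the 1RM and EMG outcomes. State that HRR, a listed secondary outcome, has no reported result if that is so.
6. Reconcile the resting heart rate listing between 1.3, 2.5, SAP 1 and v1.0, and label it as added if v1.0 does not list it.

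The cost is one file check, a short addendum and wording changes in four places (Executive Summary, 3.3.1, Discussion and 4.6), plus the outcome-list reconciliation and any p-values not yet printed. If HRR data exist, there is one further paired analysis. No new data collection is needed.

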## 2. Analysis Populations

- Intention-to-Treat (ITT): All 23 enrolled participants
- Per-Protocol (PP): Participants with  $\geq 80\%$  session adherence (actual adherence was 94.9%, so PP  $\approx$  ITT)
- Safety population: All participants who received at least one training session

## 3. Primary Efficacy Analysis

- Paired t-test (or Wilcoxon signed-rank test if normality violated) comparing baseline vs. Week 6 for each 1RM exercise
- Effect size: Cohen's d (paired)
- Summary: Mean  $\pm$  SD at baseline and Week 6, mean change, 95% CI, p-value, Cohen's d

#### **4. Injury Incidence**

- Proportion of participants with  $\geq 1$  training-related injury (with 95% Clopper-Pearson exact CI)
- Injury rate per 1,000 training hours

#### **5. Secondary Efficacy Analyses**

All continuous secondary endpoints analysed exactly as primary (paired t-test/Wilcoxon, Cohen's d, 95% CI)

#### **6. Missing Data**

No missing primary outcome data expected (all 23 participants completed the study). If any missing values occur, listwise deletion will be used (sensitivity analysis with last-observation-carried-forward if  $>5\%$  missing).

#### **7. Multiplicity**

No adjustment for multiplicity is planned (exploratory single-arm study).

#### **8. Interim Analysis**

None planned.

#### **9. Software**

IBM SPSS 29 or R 4.4.x

#### **10. Tables & Figures (to be produced)**

Exactly the same tables and figures that already appear in your final report (Tables 2–5, Figures 1–4).

Approved by:

---

[name] (PI)

---

Date: 30 November 2024

---

[name] (Statistician)

---

Date: 30 November 2024

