## **EXECUTIVE SUMMARY**

This prospective, single-center, interventional study evaluated the efficacy of the **5-Line Principle of Balanced Intensity Training (BPIT)** in improving physical performance and reducing injury risk over a 6-week training period.

- **Participants:** Twenty-three participants (18 males aged 22-48 years, 5 females aged 20-33 years) completed the study with a mean adherence rate of 94.9%.
- **Key Findings:** The BPIT protocol demonstrated statistically significant improvements across all measured outcomes, including:
  - Strength gains of 15-25%.
  - Enhanced autonomic function (HRV increase of 12.67 ms).
  - Improved biomechanical efficiency (knee valgus reduction of 17.9%).
  - A low injury incidence rate of 4.3%.
- **Conclusion:** These findings support the BPIT method as an effective and safe training approach for diverse populations.

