#### 3.2.2 Injury Incidence

Only one mild muscle strain was reported, resulting in an injury incidence rate of 4.3% (1/23 participants) and an injury rate of 2.54 per 1000 training hours.

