## 4. DISCUSSION

The BPIT protocol is highly effective, demonstrating statistically significant and clinically meaningful improvements across all measured outcomes, with large effect sizes ( $d$  ranging from 2.97 to 4.76). The low injury incidence rate (4.3%) supports its safety profile. The intensity cycling likely optimizes the balance between training stress and recovery, leading to enhanced adaptation.

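### SAP section 10 orders tables that lack the intervals and p-values SAP sections 3 to 5 require; the omission that matters is the exact interval for injury, 0.1% to 21.9%

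*SAP*

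**What the plan says.** SAP section 3 lists what must be reported for each of the three lifts. Besides the baseline and Week 6 summaries, it requires "mean change, 95% CI, p-value, Cohen's d", with d specified as the paired version. SAP section 5 carries this over to the rest: "All continuous secondary endpoints analysed exactly as primary". Its parenthesis names the 95% interval again. It does not repeat the p-value, which comes in through the reference to the primary analysis.

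SAP section 4 requires the proportion of participants injured "with 95% Clopper-Pearson exact CI", plus a rate per 1,000 training hours. It asks for no interval on the rate.

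SAP section 10 then sets the outputs as "Exactly the same tables and figures that already appear in your final report" and identifies these as Tables 2 to 5 and Figures 1 to 4.

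Protocol section 3.2.2 reports one mild strain, "resulting in an injury incidence rate of 4.3% (1/23 participants"), and 2.54 per 1,000 training hours. The Discussion says "The low injury incidence rate (4.3%) supports its safety profile", and the Conclusions describe the evidence for safety as strong. On efficacy, the Executive Summary claims "statistically significant improvements across all measured outcomes", and the Discussion speaks of the method "demonstrating statistically significant and clinically meaningful improvements across all measured outcomes".

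**The concern.** Sections 3 to 5 of the SAP ask for items that the tables ordered in section 10 do not contain. Someone who follows section 10 to the letter reproduces tables that fall short of the same plan's requirements, and both primary outcomes are affected.

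The stake is small for the continuous outcomes and larger for injury. A single event in 23 people says little about the true incidence, and the exact interval is what would show the reader this. Without it, 4.3% reads as an established low rate, and the safety statements in the Executive Summary, Discussion and Conclusions rest on a bare point estimate.

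**Working it through.** **Plan against tables.** The column headings in the Protocol are intact, so this is a direct comparison. The last column is not in the documents. It is derived below from the printed d.

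| Row | 95% CI shown | p shown | Implied 95% CI for mean change |
|---|---|---|---|
| Squat (Table 2) | no | no | 20.0 to 25.8 kg |
| Bench press (Table 2) | no | no | 13.9 to 18.3 kg |
| Deadlift (Table 2) | no | no | 21.9 to 27.3 kg |
| Resting heart rate (Table 3) | no | yes | -6.67 to -5.37 bpm |
| RMSSD (Table 3) | no | yes | 11.52 to 13.82 ms |
| Knee valgus (Table 4) | no | yes | -2.49 to -1.99 deg |
| Spinal curvature (Table 4) | no | yes | -0.81 to -0.61 deg |
| Rectus abdominis (Table 5) | no | no | 9.93 to 12.31 %MVC |
| Quadriceps (Table 5) | no | no | 11.09 to 13.37 %MVC |

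The interval is absent from 9 of 9 rows and the p-value from 5 of 9. The captions of Figures 1 to 4 describe individual lines with mean and SD bars, so the figures do not supply the intervals. No listed table or figure covers injury.

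**Injury: the documents' own figures.** Inputs are 1 event and 23 participants (Protocol 3.2.2), three 60-minute sessions a week for six weeks (2.4), and 94.9% adherence (3.1).

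- Proportion: 1/23 = 4.35%, matching the printed 4.3%.
- Hours: 23 × 18 × 0.949 = 392.9. Rate: 1000/392.9 = 2.545. This agrees with the printed 2.54 once rounding of the adherence figure is allowed for (at 94.95%, 1000/393.1 = 2.544).

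**Injury: the missing interval.** The Clopper-Pearson limits for 1/23 are:

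- Lower: the p at which P(X ≥ 1) = 0.025, that is Beta(0.025; 1, 23) = 0.0011.
- Upper: the p at which P(X ≤ 1) = 0.025, that is Beta(0.975; 2, 22) = 0.2195.

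Check of the upper limit: (1 - p)^22 × (1 + 22p) at p = 0.2195 is 0.025. The interval is 0.1% to 21.9%. The upper limit corresponds to about 5 in 23 (0.2195 × 23 = 5.05).

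**Continuous outcomes: what the printed figures imply.** SAP section 3 specifies a paired d, that is mean change divided by SD of change. The other common definitions do not fit Table 2:

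| Lift | Printed d | Change / baseline SD | Change / average SD |
|---|---|---|---|
| Squat | 3.44 | 1.02 | 0.90 |
| Bench press | 3.12 | 0.76 | 0.69 |
| Deadlift | 4.01 | 0.87 | 0.80 |

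Taking the printed d as paired, SD of change = change/d, the interval is change ± 2.074 × SD/√23, and t = d × √23 on 22 degrees of freedom.

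- Squat: SD = 22.91/3.44 = 6.66; 22.91 ± 2.88; t = 16.50.
- Bench press: SD = 16.11/3.12 = 5.16; 16.11 ± 2.23; t = 14.96.
- Deadlift: SD = 24.60/4.01 = 6.13; 24.60 ± 2.65; t = 19.23.
- Rectus abdominis: t = 4.05 × √23 = 19.42. Quadriceps: t = 4.65 × √23 = 22.30.

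All five rows without a printed p-value would therefore show p < 0.001.

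**The case against.** The strongest reply is that section 10 is only a list of display items. It does not say that nothing else will be reported, and it does not cancel sections 3 to 5. A single proportion can properly be given in text, and section 4 binds whether or not an injury table is listed. This stands in part. A reader might infer that the SAP drops injury from its outputs altogether, and the documents do not support that. But calling for exactly the existing tables leaves no room for the columns that sections 3 and 5 require, and the text result in 3.2.2 does lack its interval.

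A second reply is that the attached statistical results file cited in Appendix C may hold all the missing values. It may; the file is not among the documents. The shortfall is shown only for the Protocol text and Tables 2 to 5. Section 10 does not call for that file's contents, so the inconsistency within the SAP remains.

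A third is that the missing p-values change nothing. That is right. A reader might infer that the claims of significance across all outcomes are unfounded because the primary table shows no p-value. The printed effect sizes imply otherwise.

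A reader might also infer that precision for the lifts is lost. It is not, provided the printed d is the paired d that the SAP specifies.

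**Conclusion.** The point holds as an inconsistency between SAP section 10 and SAP sections 3 to 5, carried through to the reported tables. Its extent is 9 of 9 rows without an interval, 5 of 9 without a p-value, and the one injury proportion without its exact interval.

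The material consequence is confined to injury. With 1/23 and an exact 95% interval of 0.1% to 21.9%, the data are compatible with a very low incidence and with about one in five, so 4.3% alone is weak support for a safety conclusion. The interval does not show the programme to be unsafe either. This result needs no assumption beyond the binomial model that section 4 already adopts.

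The implied intervals and p-values for the continuous outcomes do rest on an assumption: that the printed d values are correct and paired. They indicate that no conclusion about significance would change, but they do not replace values computed from the participant data.

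**What to change.** Amend SAP section 10 to call for Tables 2 to 5 with the 95% confidence interval and p-value in every row, computed from the participant data, together with Figures 1 to 4. Add the injury result to the list: n/N, percentage, Clopper-Pearson 95% interval, and rate per 1,000 training hours. A line of text is enough for this; a separate table is optional.

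In the Executive Summary, section 3.2.2 and the Discussion, report injury incidence as 1/23 (4.3%; exact 95% CI 0.1% to 21.9%). Temper the safety statements in the Discussion and Conclusions to match that interval.

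The cost is one amended SAP sentence, added table columns from data already held, one interval in three places, and some rewording. Because sections 3 to 5 already require these items, completing the tables and text cures the substantive gap. The section 10 amendment removes the instruction that conflicts with them.

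### The SAP was written with results in hand but reads as a forward plan, and the report concludes efficacy, safety and reduced injury risk from an exploratory single-arm study

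*SAP*

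**What the plan says.** **Timing of the SAP.** Section 10 is headed as outputs still to be produced, but defines them as "Exactly the same tables and figures that already appear in your final report", namely Tables 2–5 and Figures 1–4. Section 2 justifies the per-protocol set by noting that "actual adherence was 94.9%, so PP" is about the same as ITT. Section 6 says no missing primary data are expected because "all 23 participants completed the study". Both approval dates are 30 November 2024, which the protocol's registration appendix also gives as primary completion.

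**Endpoints.** Protocol section 1.3 gives the secondary aim as "To evaluate the impact on heart rate variability (HRV), heart rate recovery (HRR), muscle activation patterns (EMG" and joint biomechanics. Section 2.5 lists "Change in HRV (RMSSD); Change in HRR; Change in EMG (rectus abdominis, quadriceps", followed by knee valgus and spinal curvature. SAP section 1, whose heading says the objectives come directly from the protocol, opens its secondary list with "Change in resting heart rate and heart rate variability" and keeps HRR only if it was measured.

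**Status and conclusions.** SAP section 7 states "No adjustment for multiplicity is planned (exploratory single-arm study". Protocol section 4.6 concedes that there was no control group. The Executive Summary, the text under Table 2, the text under Table 4, section 4 and section 5 nevertheless credit BPIT with efficacy, safety, or lower injury risk or risk factors. SAP section 4 requires the injury proportion "with 95% Clopper-Pearson exact CI"; protocol section 3.2.2 gives 4.3% (1/23) and 2.54 per 1,000 training hours without an interval.

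**The concern.** An SAP has evidential value because it fixes endpoints and tests before the results are known. This one cites results and is still phrased as a plan, so a reader could take it as support for an endpoint list that follows the reported tables.

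The larger problem is what the report concludes. The primary objective has two parts: higher 1RM and fewer training-related injuries. Both are stated as effects of BPIT. A change from baseline to Week 6 in one group cannot separate BPIT from test familiarisation, time or other training. A reduction in injury also needs a rate to compare with, and neither document gives a control, historical or pre-study rate. Nor is it consistent to call the study exploratory when declining multiplicity adjustment and then to present its results as strong evidence. Both co-primary conclusions are affected.

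**Working it through.** **1. Timing.** This is a check of the text. Tables 2–5 hold the strength, physiological, biomechanical and EMG results. SAP section 10 says they already exist, and sections 2 and 6 state observed adherence and completion. Each of these shows that results were in hand. The identical approval and primary completion dates fit this but are not needed to establish it.

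**2. Endpoints side by side.**

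| Measure | Protocol 1.3 and 2.5 | SAP section 1 | Report tables |
|---|---|---|---|
| HRR | Listed outright | Conditional on measurement | None |
| Resting heart rate | Not listed | Listed | Table 3 |

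Both departures move the SAP list towards what was reported.

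**3. Injury proportion.** Inputs: x = 1, n = 23 (protocol 3.2.2).
- 1/23 = 4.35%, which agrees with the stated 4.3%.
- Clopper-Pearson lower limit: 2.5% quantile of Beta(1, 23) = 0.0011.
- Clopper-Pearson upper limit: 97.5% quantile of Beta(2, 22) = 0.2195.
- Exact 95% CI: 0.1% to 21.9%.

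**4. Injury rate.** Inputs: three 60-minute sessions a week for six weeks (protocol 2.4), 94.9% adherence (protocol 3.1).
- Scheduled hours: 23 × 18 = 414. Attended: 414 × 0.949 = 392.9.
- Rate: 1000/392.9 = 2.545 per 1,000 hours. With 393 attended sessions (393/414 = 94.93%) it is 2.5445, which rounds to the stated 2.54.
- Hours implied by the stated rate: 1000/2.54 = 393.7.
- Exact Poisson 95% limits for one event are 0.0253 and 5.572. Divided by 393.7 hours, they give 0.06 to 14.2 per 1,000 hours.

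**5. How little one injury in 23 says.** P(X ≤ 1) = (1 − p)^23 + 23p(1 − p)^22. The true six-week risks below are assumptions, not figures from the documents.

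| Assumed risk p | P(at most 1 injury in 23) |
|---|---|
| 5% | 68% |
| 10% | 32% |
| 15% | 12% |
| 20% | 4% |

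**6. Strength.** Mean change divided by baseline mean (Table 2):
- squat 22.91/109.32 = 21.0%
- bench press 16.11/76.57 = 21.0%
- deadlift 24.60/123.10 = 20.0%

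Taking Table 2's Cohen's d as the paired version named in SAP section 3, t = d × √23: 3.12 × 4.796 = 15.0 for bench press, 3.44 × 4.796 = 16.5 for squat and 4.01 × 4.796 = 19.2 for deadlift. Chance is not a plausible explanation for these changes. The open question is their cause, which no reanalysis of one arm can settle.

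**The case against.** **The true protocol may not be in view.** The text supplied as the protocol is a completed report, and its Appendix D lists a separate v1.0 protocol file. Resting heart rate or conditional HRR may be in that file. This stands as a limit: what v1.0 prespecified cannot be judged, and selective choice of endpoints is not shown. The SAP list still disagrees with sections 1.3 and 2.5 as supplied, and an earlier plan would not make this SAP prospective.

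**The late timing is visible, and no document claims prespecification.** That is correct, and nothing suggests concealment. The defect is a retrospective document with no post hoc label and forward-looking wording.

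**The late SAP changes no strength p-value.** With t between 15 and 19, neither the choice between t-test and Wilcoxon nor a multiplicity adjustment would alter significance. This stands, and the seriousness of the point rests mainly on attribution and on the injury claim.

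**Limitations are acknowledged.** Section 4.6 names the missing control group, small sample and short duration. Section 5 then draws its conclusions as if they did not apply.

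**Smaller points.** The appendices with participant data and statistical results were not supplied, so an HRR result or the injury interval may be there; what can be said is that no table or visible text gives them. The Table 4 text speaks of injury risk factors rather than injuries, so it is the weakest of the five examples.

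**Conclusion.** The concern holds and needs correction. The SAP is a post hoc document and does not show that endpoints or tests were fixed before results were known. One listed secondary outcome (HRR) has no result in the tables or visible text, and one reported outcome (resting heart rate) is in neither protocol 1.3 nor 2.5.

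The causal conclusions are not supported by the design. Mean 1RM rose by 20.0% to 21.0%, but the share due to BPIT is not estimable. The injury data are compatible with a six-week risk from 0.1% to 21.9%, so about 1 in 5 is not excluded, and no reduction can be estimated. The proportion interval assumes independent participants with a common risk. The rate interval assumes a Poisson count over about 394 hours. The statements on endpoints rest on the documents supplied.

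**What to change.** **SAP.** Keep the approved text and add a dated statement that it is post hoc. State when data and results were accessed, which endpoints differ from protocol 2.5 (HRR made conditional, resting heart rate added), and whether HRR was measured.

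**Report.**
- Carry the exploratory label into the Executive Summary and sections 4 and 5.
- In the Executive Summary, the text under Table 2, and sections 4 and 5, replace the efficacy claims with: *uncontrolled within-participant changes from baseline to Week 6; effect attributable to BPIT not estimable*.
- In the Executive Summary and sections 4 and 5, replace the safety and injury-reduction claims with: *one training-related injury in 23 participants (4.3%, exact 95% CI 0.1% to 21.9%); with no comparator, no reduction in injury risk can be estimated*. Give the same interval in section 3.2.2.
- Under Table 4, state only the observed changes.
- Section 1.2 on ClinicalTrials.gov says the study is registered, while the registration appendix says registration is in progress. Correct the former and state that registration was still pending when results were reported.

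**Cost.** One dated statement, rewording, and one interval that SAP section 4 already requires. No new data are needed. The conclusion becomes weaker.
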